##### **4.2.2.3. Other Endpoints**

The other endpoints in Phase III are:

- Time to first extubation
- Proportion of patients achieving 8-point ordinal scale score 3 or below (patients alive and free of respiratory failure) at day 15 and day 28
- Glasgow Outcome Scale score assessed at study day 60
- Quality of life assessed by EuroQol 5-D (EQ-5D) at study day 60.

## 5. STUDY DESIGN

### 5.1. Overall Design

This is a pragmatic, adaptive, randomized, multicenter phase II/III study evaluating IFX-1 for the treatment of COVID-19 related severe pneumonia. The study consists of two parts: Phase II, an open-label, randomized, 2-arm phase evaluating BSC + IFX-1 (Arm A) and BSC alone (Arm B); and Phase III, a double-blind, placebo-controlled, randomized phase evaluating SOC + IFX-1 (Arm A) and SOC + placebo-to-match (Arm B). The SOC includes VTE prophylaxis at a minimum, and may include other international and country-specific recommended treatments for COVID-19 per the locally adopted treatment recommendations. An independent safety monitoring board in phase II part and an independent data monitoring board (IDMC) in phase III part are established to monitor the patients' safety in an ongoing manner (see Sections 5.3 and 5.5).

At the time of writing of Protocol Version 2.0, Phase II of the study has been completed and all 30 patients have been treated (15 in Arm A [BSC + IFX-1] and 15 in Arm B [BSC alone]). A preliminary interim analysis has been performed to assess the clinical benefit of the treatment using the assessed clinical parameters. An expert committee (EC) has monitored safety and the supported re-definition of clinical endpoint(s) for Phase III.

In Phase II, patients in Arm A were treated with a maximum of 7 IV doses of IFX-1 800 mg over a period of 29 days. The first 5 treatments at days 1, 2, 4, 8, and 15 were administered to all patients randomized into Arm A. Treatment at day 22 was only administered in the event that a patient has not been extubated and discharged from ICU. In case a patient's clinical situation worsened after day 8, although an initial clinical benefit was observed, one additional administration of 800 mg IFX-1 between day 11 and 13 could have been given at investigator discretion. Loss of clinical benefit could in this situation relate to the exceptionally high C5a levels observed in some cases of COVID-19 related pneumonia and associated shortened IFX-1 half-life.

Phase III of the study will randomize up to 400 patients with one interim analysis for stopping for futility. A total of 180 patients are planned to be randomized into Arm A and Arm B using a 1:1 allocation ratio for the first stage; based on results of the interim analysis, up to an additional 180 patients are planned to be randomized using the same allocation ratio for the second stage. Additional patients will be randomized under the following conditions:

- For patients who were erroneously randomized (screening failures) and did not get IMP treatment.
- For patients who were randomized but consent was withdrawn (either by the patient or patient representative) within the first 48 hours after randomization, irrespective of whether IMP was administered or not.

The primary statistical analysis will be based on all randomized patients except patients randomized in error (reason for early termination documented as “Randomized by mistake” in the eCRF) who did not get IMP treatment.

In Phase III, patients will be treated with a maximum of 6 IV doses of IFX-1 800 mg (Arm A) or placebo (Arm B) at days 1, 2, 4, 8, 15, and 22, as long as the patient is still in the hospital (even if discharged from the ICU).

Patients will be assessed for quality of life using the EQ-5D.

Patients will be followed for survival and their clinical status assessed by the Glasgow Outcome Scale.

### **5.1.1. Method of Treatment Assignment**

In Phase II, patients were centrally assigned to a treatment arm by the Investigator via the randomization module of the electronic case report form (eCRF). The investigational medicinal product (IMP) was assigned to each patient by the investigator at the investigation site. Sites were each given a randomization block and instructed to assign the first patient to Arm A, the second patient to Arm B, etc. The site recorded the IMP assignment on the applicable eCRF, if required.

In Phase III, patients will be centrally assigned to a treatment arm by the investigator via an Interactive Web Response System (IWRS). IMP will be assigned to each patient by the IWRS.

IMP shipment to sites will be automatically triggered by the IWRS, and will be initiated, maintained, and controlled by the IWRS.

IMP is dispensed at the study visits as summarized in the schedule of assessments (SoA, Table 1 and Table 2).

### **5.1.2. Blinding**

Phase II of the study was open-label and randomized, while Phase III will be double-blind, placebo-controlled, and randomized.

## **Phase III: Emergency Identification of Investigational Medicinal Product**

Breaking of the treatment-assigned blind will be performed in the IWRS (please refer to the Interactive Response Technology Study User Guide for instructions on unblinding). Any premature breaking of the blind should be confined to emergency cases in which knowledge of the IMP received is necessary, e.g., to be able to provide appropriate emergency medical treatment. Before breaking the blind, the investigator should contact the medical monitor whenever possible, unless this would delay the emergency treatment. Subject safety must always be the primary consideration when determining whether to break the blind.

Investigators will be provided with the appropriate IWRS access to unblind the treatment assignment of an individual subject.

If a subject's treatment assignment is unblinded, the required personnel will receive an alert from the IWRS. In addition, the investigator must inform the medical monitor within 24 hours of breaking the blind and the subject will be discontinued from further IMP treatment. The date and reason why the blind was broken must be provided by the investigator and recorded in the source documentation and in the eCRF, as applicable.

## **5.2. Patient Enrollment**

In Phase II, patients were randomized to Group A or B. The maximum number of randomized patients in Phase II was set to 30. There was a recruitment stop after the planned number of patients for Phase II were enrolled. After the preliminary interim analysis of Phase II was performed and the EC recommended to proceed, the number of patients for Phase III was calculated according to the established hypothesis. For details on the role of the EC, see Section 5.4.

In Phase III, 180 patients are planned to be randomized into Arm A and Arm B using a 1:1 allocation ratio for the first stage; based on results of the interim analysis, up to an additional 180 patients are planned to be randomized using the same allocation ratio for the second stage.

For patients randomized in error (screening failures) and patients for whom consent is withdrawn within 48 hours after randomization, additional patients will be randomized. Depending on the number of patients meeting criteria for additional randomization, more than 360 patients will be randomized but not more than 400.

## **5.3. Independent Safety Monitoring Board for Phase II**

An independent Safety Monitoring Board (iSMB) was constituted to support safety surveillance in both treatment arms throughout Phase II and Phase III of the study. The committee included at least 2 Intensive Care specialists not involved as investigators in this study and an independent statistician.

The iSMB monitored the safety of all patients regularly, after 10, 20, and 30 patients completed their treatment in Phase II. At each review, the iSMB recommended on continuing or ending the study. After completion of Phase II (30 patients), the iSMB has assessed the totality of available data of all patients and has recommended on proceeding to Phase III (see Section 3.2.3).

## **5.4. Expert Committee for Phase II**

An EC was constituted to support efficacy surveillance in both treatment arms throughout Phase II of the study. The committee included the clinical study monitor and at least 3 Intensive

Care specialists involved in the treatment of COVID-19 affected patients (Coordinating Investigator included).

The committee monitored the efficacy of all patients regularly, after 10, 20, and 30 patients completed their treatment. At each review, the EC was able to recommend on continuing or ending the study.

After completion of Phase II (30 patients), the EC assessed the totality of the data of all patients, taking into account the recommendations of the iSMB and recommend proceeding to Phase III, assessed appropriateness of the endpoints and scheduled assessments, and supported establishing an adequate hypothesis for Phase III.

The EC has stopped meeting at the beginning of Phase III (i.e., at the time of writing of Protocol Version 2.0).

## **5.5. Independent Data Monitoring Committee for Phase III**

In Phase III, the iSMB from Phase II will continue as an Independent (Clinical Trial) Data Monitoring Committee (IDMC). The IDMC will meet every 3 months throughout Phase III of the study to further assess safety. In addition, the IDMC will perform an unblinded assessment of the data of the interim analysis and will make recommendations on whether to continue the study or not according to the predefined early stop criterion (see Section 10.2.3.5). All available data will be provided to the IDMC before each meeting. Details will be described in a separate IDMC Charter.

## **5.6. Patient and Study Completion**

### **5.6.1. Phase II**

#### **5.6.1.1. End of Treatment and Follow-up**

End of treatment (EOT) was defined as last planned administration or discontinuation of IMP for other reasons. The EOT telephone visit (Follow-up Visit [FUV] 1) was to occur 28 days after last study drug administration in Phase II. The visit information obtained via the telephone call (e.g., AEs, survival status) was to be recorded.

Discontinuation of study treatment did not represent withdrawal from the study.

For details on treatment discontinuation criteria, see Section 7.2.4.

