### Number of Patients:

**Phase II:** 30 patients (15 arm A+ 15 arm B)

**Phase III:** Total of 180 patients (approximately 90 per arm) in Stage 1 and 180 patients (approximately 90 per arm) in Stage 2 are planned. The assumed rate for randomization of additional patients, i.e. patients randomized in error (screening failures) and patients for whom consent is withdrawn within 48 hours after randomization, is 10%. The planned maximum number of patients in the study is 400, 200 patients per treatment arm. The sample size ensures 90% power to show superiority of IFX-1 for the primary endpoint of 28-day all-cause mortality. Sample size calculations were based on the assumption that IFX-1 can reduce a 30% mortality under SOC by 50% to a mortality of 15% and that at least 360 patients are evaluable for the primary endpoint for the final analysis.

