**Reference Therapy, Dose, and Mode of Administration:****Phase II**

In Arm B, patients received BSC alone.

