## CONFIDENTIAL

## 2. SCHEDULE OF ASSESSMENTS

Table 1 Schedule of Assessments: Phase II

	Treatment Period (Maximum 4 Weeks)														Follow-up Period (2 Months)(Telephone)		
	Screening Period	Days -2 – 0	Day 1	Day 2	Day 3	Day 4	Day 5	Day 7	Day 8	Day 9	Day 11	Day 13	Day 15	Day 22	Day 29/ Discharge	EOT = FUV 1	EOS= FUV 2
																28 days after last IFX-1 treatment	28 days after FUV 1
Deferred Informed consent a									X								
Inclusion/exclusion criteria	X																
Demographics, medical/disease history, prior medications		X															
Disease/response assessments b	X				X		X	X		X	X	X	X	X	X		
Imaging c	X					X			X				X		X		
Concomitant disease	X																
Concomitant medications	X	X			X			X		X			X	X			
Blood sample for plasma complement and PK assessment d		X	X						X						X		
IV administration of IFX-1 e			X	X		X			X		(x)		X	(x)			
Safety Assessments																	
Weight	X				X			X					X	X	X		
Height	X																
Physical examination	X				X			X					X	X	X		
Safety laboratory test f		X	X		X			X		(x)		X	X	X			

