#### **8.1.3.1. Adverse Events Assessments**

Adverse events were to be assessed throughout the study from the time of enrollment to the EOT visit as specified in the SoA (Table 1). For details on AE collection and reporting, see Section 9.1. The investigator should have taken appropriate measures to follow all AEs until clinical recovery was complete and laboratory results had returned to normal, or until progression had been stabilized, or until death, in order to ensure the safety of the patients. This may imply that observations would continue beyond the last planned visit per protocol, and that additional investigations may have been requested by the sponsor. When study treatment was prematurely discontinued, the patient's observation was to be continued until the EOT visit for that patient as defined by the protocol.

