#### 10.1.3.2. Safety Analyses

The occurrence of AEs was to be compared between treatment arms. Treatment-emergent AEs (TEAEs) were to be analyzed according to the number and percentage of patients who had a

TEAE, as well as the number of TEAEs with the respective Medical Dictionary for Regulatory Activities (MedDRA) System Organ Class and Preferred Term. Additionally, the number and percentage of patients with TEAEs were to be further grouped by severity and causal relationship. The number and percentage of patients with SAEs and the number of SAEs were to be analyzed. Where AEs were grouped by severity or relationship, the maximum severity/relationship per patient and class of AE was to be considered.

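### Phase II end of treatment, follow-up visits and AE closing date are counted from the last IFX-1 dose, which Arm B never receives, so equal AE follow-up between the arms is not assured

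*Combined protocol and SAP*

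**What the plan says.** All references are to the Phase II text of the protocol (Version 4.0; the end-of-treatment text is the same in Version 2.0).

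- **Control arm.** Synopsis, Reference Therapy: "In Arm B, patients received BSC alone". There was no placebo. The arm sizes are "30 patients (15 arm A+ 15 arm B".
- **End of treatment.** Section 5.6.1.1: "End of treatment (EOT) was defined as last planned administration or discontinuation of IMP for other reasons". The visit itself is timed as follows: "The EOT telephone visit (Follow-up Visit [FUV] 1) was to occur 28 days after last study drug administration in Phase II". Table 1 places the same visit "28 days after last IFX-1 treatment".
- **End of study visit.** Table 1 places follow-up visit 2 "28 days after FUV 1".
- **AE period.** Section 8.1.3.1: "Adverse events were to be assessed throughout the study from the time of enrollment to the EOT visit". Section 9.1, which is not split by phase, instead ends AE reporting 30 days after the last IFX-1 administration.
- **Analysis.** Section 10.1.2 uses all randomized patients. Section 10.1.3.2: "The occurrence of AEs was to be compared between treatment arms". SAEs are to be tabulated as well.
- **Dosing in Arm A.** Section 7.2.1.1 gives doses on days 1, 2, 4, 8 and 15 to all Arm A patients. The day 22 dose went only to those not yet extubated and discharged from ICU.
- **Reported result.** Section 3.2.3 says that serious AE rates were similar in the two groups. It states no observation period for these events.

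**The concern.** Both rules that close the AE period, 28 days in Sections 5.6.1.1 and 8.1.3.1 and 30 days in Section 9.1, need a date of last study drug. Arm B has no such date, and no substitute appears in Section 5.6.1, Table 1, Section 8.1.3.1, Section 9.1 or Section 10.1. As written, the rule cannot be applied to half of the randomized patients, although those patients are one side of the planned comparison.

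Within Arm A, the length of the window depends on what happens after randomization: a patient who recovers slowly enough to receive the day 22 dose is observed for a further week. A count or percentage of patients with an AE rises with time observed. The between-arm figures can therefore be read as a safety comparison only if the two arms were observed for similar periods.

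Frequency of TEAEs and SAEs is a named Phase II secondary endpoint (Section 4.2.1.2), and the current protocol still carries the statement on serious AE rates.

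**Working it through.** Phase II has no sample size or power figure to reproduce (Section 10.1.1). The check is calendar arithmetic on the protocol's own rules.

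**Consistency of the inputs**
- Arm B share: 15 / 30 = 50%.
- Follow-up after the last dose: 28 + 28 = 56 days, which fits the two-month follow-up period in Table 1 and Section 5.6.1.2.

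**Formulas**
- Follow-up visit 1 = day of last dose + 28
- Follow-up visit 2 = follow-up visit 1 + 28
- End of AE reporting under Section 9.1 = day of last dose + 30

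**Arm A, planned dosing**

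| Last dose | Visit 1 (AE end, 28-day rule) | Visit 2 | AE end, 30-day rule |
|---|---|---|---|
| Day 15 | 15 + 28 = 43 | 43 + 28 = 71 | 15 + 30 = 45 |
| Day 22 | 22 + 28 = 50 | 50 + 28 = 78 | 22 + 30 = 52 |

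A patient who stopped dosing early would close sooner. A last dose on day 8, for example, gives day 36 under the 28-day rule and day 38 under the 30-day rule.

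**Arm B.** There is no day of last dose, so none of the three dates can be computed. The last visit with a defined time is Day 29/Discharge.

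**Size if Arm B closed at day 29.** This closing day is an assumption; the documents give no rule.
- 28-day rule: 43 / 29 = 1.48 and 50 / 29 = 1.72, that is, 14 and 21 more days in Arm A.
- 30-day rule: 45 / 29 = 1.55 and 52 / 29 = 1.79, that is, 16 and 23 more days in Arm A.

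**Size if sites gave Arm B dates matched to Arm A.** This is also an assumption. The difference could be near zero.

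**The case against.** The strongest reply is that the gap is narrower than it first appears and may already be closed elsewhere. Four parts of this stand.

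1. Table 1 has fixed study-day visits with AE collection through Day 29/Discharge that are not restricted to Arm A, and AE assessment starts at enrollment in both arms. A reader might infer that Arm B has no AE window at all. The documents do not support that: only the later period and the closing date are undefined.
2. A reader might infer that the reported comparison did use unequal follow-up. No section says so. Section 10.1.3 is a summary of a Phase II SAP that is not among the documents and may set an Arm B cut-off or a TEAE definition for untreated patients. Section 3.2.3 describes treatment for up to 28 days and clinical parameters until day 28, and nothing shows that events after day 29 entered the statement on serious AEs.
3. A reader might infer a bias in favour of IFX-1, or that the benefit/risk argument rests on the comparison of serious AE rates. A longer Arm A window would raise Arm A counts and so count against IFX-1. The serious AE statement is in Section 3.2.3. Section 3.3 cites instead fewer pulmonary embolisms reported as SAEs, and a longer Arm A window would not produce that finding.
4. Phase II was exploratory and is finished, so new visit dates cannot change what was collected.

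A literal reading of Appendix 3, which ties an AE to use of study drug, would leave Arm B with no AEs. Section 3.2.3 nevertheless reports pulmonary embolisms as SAEs in Arm B. Some working rule was therefore applied, but the documents do not state it.

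The reply does not supply an anchor for Arm B. Nor does it remove the dependence of the Arm A window on clinical course.

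**Conclusion.** The point holds as a lack of assurance, not as a demonstrated imbalance. For 15 of 30 patients the protocol gives no date for end of treatment, either follow-up visit or the close of AE collection, while Arm A patients given the planned doses close at day 43 or 50, or at day 45 or 52 under the 30-day rule.

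The possible imbalance ranges from near zero, with matched dates, to about 1.5 to 1.8 times the ascertainment time, with Arm B closed at day 29. Both ends rest on assumptions about Arm B. Turning the ratio into a difference in event percentages would need an event rate and a hazard shape that the documents do not give.

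The consequence is limited to how the Phase II AE and SAE comparison can be read. The 28-day mortality and the fixed-day oxygenation and response endpoints do not use this anchor. Phase III follow-up visits are counted from randomization, and its control patients receive placebo doses.

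**What to change.** Phase II is complete, so the change belongs in analysis and reporting.

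- In Section 10.1.3.2, base the between-arm AE and SAE comparison on events with onset from randomization to day 28 in both arms. List later events separately.
- Report the anchor actually used for Arm B, which of the 28-day and 30-day rules was applied, and AE observation time by arm. Observation time will also show whether collection ended before day 28 for anyone discharged early.
- Qualify the statement in Section 3.2.3 on serious AE rates with the observation period behind it, or restate it for the common window.

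The cost is one re-tabulation by onset date for 30 patients, plus wording. The downside is that late Arm A events move from the comparison to a listing. No clinical management changes.

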#### **5.6.1.2. End of Study**

Patients were to be followed for survival using the Glasgow Outcome Scale until the end of study (EOS) visit (FUV 2). If required, information could have been obtained by a telephone call.

The EOS for the individual patient was defined as the date of the last contact of the 2-month follow-up period, date of death, date of consent withdrawal from study participation (see Section 5.6.1.3), or the date of last contact when patients were lost to follow-up (see Section 5.6.1.4).

The entire study was to end when all patients discontinued IFX-1 AND all patients ended the study as described above.

The sponsor could have prematurely terminated Phase II of the study at any time earlier than planned for the following reasons:

- Unacceptable toxicity
- Administrative reasons

#### **5.6.1.3. Consent Withdrawal/ Discontinuation of Study Participation**

A patient could have withdrawn from Phase II of the study at any time at his/her own request without the need to provide any reason(s).

If the patient withdrew from study participation, the sponsor could have retained and continued to use any data collected before such a withdrawal of consent. However, in the case of deferred informed consent, if the consent was not obtained or if a legal representative denied the patient's participation in the study, the patient was excluded and data were no longer to be used (see Section 6.3). Patients (or legal representatives) who wished to withdraw consent/discontinue the study while still on treatment should have been encouraged by the investigator to perform the EOT visit for their own safety before any further data collection for study purposes was terminated.

If a patient withdrew from the study, he/she could have requested destruction of any samples taken and not tested, and the investigator must have documented this in the site study records.

#### **5.6.1.4. Lost to Follow-up**

A patient was to be considered lost to follow-up if he or she could not be reached after hospital discharge for scheduled contacts and the study site was unable to make contact as described below.

The following actions must have been taken if a patient could not be reached:

- The site must have attempted to re-contact the patient as soon as possible after the failed first scheduled contact.
- Before a patient was deemed lost to follow-up, the investigator or designee must have made every effort to regain contact with the patient (where possible, 3 telephone calls and, if necessary, a certified letter to the patient's last known mailing address or local equivalent methods). These contact attempts were to be documented in the patient's medical record.

- Should the patient have continued to be unreachable, he/she was considered to have been withdrawn from the study with a primary reason of lost to follow-up.

